6.4 Summary of known and potential risks and benefits

6.4.1 Potential risks

Based on the literature on ^{90}Y -MS and animal studies on ^{166}Ho -PLLA-MS and the clinical data derived from the HEPAR I trial, it is concluded that, if the ^{166}Ho -PLLA-MS are administered correctly, the risk of complications is low. Although a potential risk described in the literature, no complications associated with non-target delivery of ^{166}Ho -PLLA-MS were observed in the HEPAR I trial. It has been described in the literature that, due to excessive radiation doses delivered to the liver parenchyma, “radiation induced liver disease” or “radiation hepatitis” is known to occur [32, 33]. This veno-occlusive disease can usually be managed by steroid treatment but in some cases will result in fulminant liver failure. However, the incidence of this complication is very low and has not been observed in any of the patient treated with ^{166}Ho -RE in the safety study. The risk of mild side effects associated with the macroembolic effect of radioembolization is significant but transient, and usually well managed by outpatient medication (see Chapter 7)

6.4.2 Potential benefits

In short, the use of radioactive microspheres administered intra-arterially as radionuclide therapy for liver malignancies can overcome disadvantages of external beam radiation, which is limited by the radiosensitivity of healthy liver tissue. Microspheres have the potential to provide treatment to previously untreatable patients.

The preclinical data (see IMDD page 22) as well as the clinical data obtained from the HEPAR I trial demonstrate that RE with ^{166}Ho -PLLA-MS is suitable for treatment of patients with liver malignancies and may have a beneficial effect on QoL and survival. However, the latter variable was not a primary endpoint of this safety study and must be further investigated in the HEPAR II trial.

6.5 Dose

The amount of ^{166}Ho radioactivity (A) that must be administered to a patient to deliver the desired absorbed liver dose can be calculated according to the following formula [23]:

$$A_{\text{Ho}166} \text{ (MBq)/LW (kg)} = \text{Liver Dose (Gy)}/15.87 \times 10^{-3} \text{ (J/MBq)} = \text{Liver Dose (Gy)} \times 63 \text{ (MBq/J)}$$

where LW is the liver weight of the patient which is determined on CT or MRI.

In this study, the patients will receive a mean liver absorbed dose of 60 Gy. The required amount of ^{166}Ho activity may then be calculated as follows:

$$A_{\text{Ho}166} \text{ (MBq)/LW (kg)} = 60 \text{ (Gy)}/15.87 \times 10^{-3} \text{ (J/MBq)}$$

$$A_{\text{Ho}166} \text{ (MBq)/LW (kg)} = 3781 \text{ (Gy} \times \text{MBq/J)}$$

$$A_{\text{Ho}166} \text{ (MBq)} = 3781 \times \text{LW (kg)}$$

The calculated dose is based on the assumption that all administered activity will be equally distributed over the whole liver. This is not a realistic assumption but a rather conservative and safe approach. Using this approach, only mild adverse events were encountered in healthy pigs treated with calculated whole liver doses up to 150 Gy [23]. The administered activity will show heterogeneous distribution over the liver enabling regeneration of relatively spared liver tissue. There were notable differences in laboratory and clinical toxicity between the 20-, 40-, and 60-Gy cohorts and the 80-Gy cohort in the HEPAR I trial.

In Table 4, "Dose (Gy) and activity (MBq) relation of holmium-166 treatment", examples of amounts of activity for typical liver weights are given for a liver absorbed dose of 60 Gy, which equates to 3.8 GBq/kg (liver weight).

Table 4. Liver weight and total radioactivity relation

Liver dose (Gy)	LW (kg)				
	1	1.5	2	2.5	3
	A (MBq)	A (MBq)	A (MBq)	A (MBq)	A (MBq)
60	3780	5670	7560	9450	11340

6.6 Accountability of radioactive device

The following flowchart demonstrates the route from preparation to disposition of the radioactive device $^{166}\text{Ho-PLLA-MS}$.

[figure not shown]

Figure 1. $^{166}\text{Ho-PLLA-MS}$ flowchart, route from preparation to disposition

Step 1 – Preparation of $^{165}\text{Ho-PLLA-MS}$ is carried out at the Good Manufacturing Practice (GMP) facility (room E.02.4.11) of the radionuclide pharmacy of the UMC Utrecht. After passing quality control, batches of $^{165}\text{Ho-PLLA-MS}$ are stored in the radionuclide pharmacy at room temperature in room E.02.411 in a vacuum dessicator.

Before neutron activation, patient dose vials are engraved with a unique identification number. A complete description of the preparation, labelling and release of ^{165}Ho -PLLA-MS is given in the IMDD (page 8-10, Appendix 2 and 3, PTC-01 and PTC-02).

- Step 2 – Neutron activation is carried out at the Reactor Institute Delft (Delft, the Netherlands). A complete description of neutron activation is given in the IMDD (page 11, Appendix 4 and 7 and PTC-04).
- Step 3 – Preparation of ^{166}Ho -PLLA-MS for patient administration is carried out at the GMP facility (room E.02.4.11) of the radionuclide pharmacy of the UMC Utrecht. A complete description of the preparation of ^{166}Ho -PLLA-MS is given in the IMDD (Appendix 4, PTC-01 and PTC-05).
- Step 4 – Administration of ^{166}Ho -PLLA-MS to the patient is carried out at the angiography suite of the radiology department. A complete description of the method of administration of ^{166}Ho -PLLA-MS is given in the IMDD (page 19-20).
- Step 5 – Measurement of radioactivity left in the administration materials is carried out at the GMP facility (room E.02.4.11) of the radionuclide pharmacy of the UMC Utrecht. Measurement is performed to calculate the net activity administered to the patient.
- Step 6 – Disposal of radioactivity is carried out in room E.00.2.19. A complete description of the disposal of radioactivity is given in the IMDD (PTC.300.02).

7. SAFETY PROFILE

The following effects are expected based on literature on treatment with ^{90}Y -MS [34-36] and form an exhaustive list of side effects observed in thousands of patients. A small selection of the following side effects has been observed in patients in the HEPAR I trial (7.1.1; 7.1.2; 7.1.3; 7.1.4). The safety profile is divided in general and technique related effects.

7.1 General side effects and complications

When the patient is treated with the proper technique, without excessive radiation to any organ, the common adverse events after receiving radioactive microspheres are fever, abdominal pain, nausea, vomiting, diarrhoea and fatigue. An abnormality of liver function tests is likely to occur. This may be up to grade 3 or 4 (CTCAE vs 4) in the case of AST/SGOT, ALT/SGPT, γ GT, ALP and LDH, without direct clinical relevance. In general these effects are transient [25]. In the HEPAR I trial, we observed AST, ALT or GGT serum level elevations up to grade 3 in 13/15 patients (87%).

7.1.1 Fatigue

Fatigue is often observed in patients. In general it does not exceed grade 2. To date, we observed fatigue in 10/15 patients (67%) treated with ^{166}Ho -RE.

7.1.2 Fever

Fever can be observed immediately after the embolization (as part of the post-embolization syndrome) or later in the follow-up. It can last for one week. The occurrence of fever later in the follow-up may be caused by the development of hepatic abscesses. To date, fever was observed in 6/15 patients (40%) following ^{166}Ho -RE, typically starting on the day of treatment, lasting 1-3 days, but may last for several weeks.

7.1.3 Abdominal pain

Right upper quadrant abdominal pain is frequently observed in patients undergoing radio-embolization, but easily managed by outpatient medication. In the HEPAR I trial, most patients experienced acute abdominal pain, which was managed with paracetamol and occasionally opiate medication. To date, one patient (7%) has been readmitted because of abdominal pain in the HEPAR I trial.

7.1.4 Gastrointestinal toxicity

Nausea and/or vomiting are known side effects of RE. Both may be controlled with anti-emetic therapy. Ondansetron (up to 3 dd 8 mg) is recommended the first 24 hours after the administration. Subsequently, metoclopramide (up to 300 mg/24 h) can be prescribed. Diarrhoea should be treated with adequate doses of loperamide (up to 16 mg/24 h). To date in the HEPAR I trial, nausea was present in 13/15 patients (87%). A selection, 8/15 patients (53%) progressed to vomitus. Diarrhoea was observed in one patient.

7.1.5 Tumour Lysis Syndrome

A major but very rare complication is Tumour Lysis Syndrome (TLS), which is caused by rapid necrosis of the tumour. Laboratory tests show high serum levels of LDH, high uric acid, high serum potassium, high phosphate and low serum calcium. In patients with solid tumours, this side effect is extremely rare. Supportive care including fluids is recommended. TLS has not been observed in patients treated in the HEPAR I trial.

7.1.6 Radiation hepatitis

The frequency of radiation hepatitis is very low in radioembolization due to the inhomogeneous distribution of the microsphere dose. Management of this serious complication, in case hepatic insufficiency occurs, consists of the use of high doses of lactulose, steroids, and, if appropriate, assessing brain pressure and relieving increased brain pressure. Hepatic insufficiency may occur in <1% of all treated patients. Radiation hepatitis (or Radiation induced liver disease) was suspected in one patient of the HEPAR I trial who had received 80 Gy.

7.1.7 Venous occlusive disease

Venous occlusive disease (VOD) may occur by radiation damage to the portal veins. This is caused by activation of the coagulation system probably due to endothelial damage. Anticoagulants such as low molecular heparin (Fraxiparin in therapeutic dosages) have been shown to be beneficial. To date, VOD has not been observed in patients in the HEPAR I trial.

7.1.8 Carcinoid crisis

In case patients with neuroendocrine tumours receive this experimental treatment, the release of neuroendocrine factors may give rise to the so called 'carcinoid syndrome'. This consists of high blood pressure, flushing and diarrhoea. This syndrome can be prevented to some extent with octreotide (300 µg i.v./24 h). Carcinoid crisis has not occurred in the HEPAR I trial.

7.1.9 Leuko- and thrombopenia

In a number of cases, transient and reversible leuko- and thrombopenia has been observed both in case of ⁹⁰Y-RE and ¹⁶⁶Ho-RE. The nadir of the laboratory toxicities can be up to grade 4.

7.2 Inadvertent non-target radioembolization

The following technique related effects are directly related to inadvertent deposition of the microspheres in organs other than the liver. None of the following events have occurred in any of the HEPAR I patients.

7.2.1 Peptic ulceration

A peptic ulcer may occur in <10% of all patients undergoing RE. The development of acute peptic ulceration is suggested by the symptoms of gastric ulcers and diagnosed by endoscopy. If this complication occurs, the patient should be treated using best standard care, including pain relief, gastric acid blocking drugs (pantoprazol i.v. up to 80 mg) and intravenous fluids. Treatment is the same as for any cause of peptic ulceration.

7.2.2 Pancreatitis

Pancreatitis may occur in 1% of all treated patients, according to the literature on RE. The post treatment nuclear images will reveal if any radioactivity may have lodged in the pancreas. Additional tests such as serum amylase are indicated if pancreatitis is suspected. If this occurs, the patient should be treated using best standard care, including pain relief, gastric acid blocking drugs (pantoprazol i.v. up to 80 mg), and intravenous fluids.

7.2.3 Radiation pneumonitis

High levels of implanted radiation and/or excessive shunting to the lung may lead to radiation pneumonitis. This may be suspected if patients develop a non-productive cough several days or weeks after the implantation of the microspheres and is diagnosed by plain X-ray or CT of the thorax. Patients should be treated with systemic corticosteroids (1 mg/kg/day) and supportive care until the condition has subsided.

7.2.4 Radiation induced cholecystitis

A rare complication is radiation induced cholecystitis, which may occur in 1-2% of all treated patients. This side effect can be expected a few weeks after the intervention. Complaints are local pain in the liver area, sometimes colicky in nature, elevated bilirubin serum levels and increased CRP. Treatment may consist of a cholecystectomy.

7.2.5 Medical treatment for inadvertent non-target radioembolization

In case a considerable portion of the dose of radioactive microspheres are deposited outside the liver, the potential toxicity may be decreased by starting treatment with the radiation scavenger amifostine (up to 200 mg i.v./m² for 7 days). It is imperative to start this treatment as soon as possible.

7.3 Other technique related complications

The following technique related complications have been reported in the literature following RE.

7.3.1 Spurious aneurysm and hematoma

As a complication of arterial catheterization in the groin, a false aneurysm (spurious aneurysm/pseudoaneurysm) may develop at the vascular access site within a few days after the procedure. This can be suspected in case of local pain and swelling in the groin, and is diagnosed with the use of ultrasound. In most cases, ultrasound-guided compression will be effective. Pseudoaneurysms less than 2 cm in size can be managed conservatively and monitored by serial imaging to confirm spontaneous resolution. First-line treatment consists of injection of bovine thrombin [37]. If the aneurysm is becoming very large and threatens or causes skin necrosis, or is expanding rapidly as it may be infected, surgical intervention should be performed. In case of vascular access site hematoma, conservative treatment is advised, because hematomas are known to resolve spontaneously in most cases within days.

7.3.2 Infection or inflammation of the arterial puncture wound

As a complication of arterial catheterization in the groin an infection/inflammation of the arterial puncture wound may develop. Adequate antibacterial treatment is warranted.

7.3.3 Iatrogenic arterial dissection and/or inadvertent embolization

Iatrogenic arterial dissection is a well-known risk of endovascular catheter treatment. Manoeuvring of a foreign object (catheter) within the vascular system comprises a risk of damage to the intimal layer of the arterial wall. As a result, an intimal dissection can occur which may or may not become symptomatic. If dissection of an (abdominal) artery becomes symptomatic, this can be managed in general by medical treatment (such as lowering of the blood pressure). Alternatively, if the dissection occurs during endovascular treatment, direct

measures can be taken to reduce the dissection by means of balloon inflation or deployment of a bare-metal stent. If these measures fail, or if the dissection becomes evident after endovascular treatment, operative surgery should be considered. Another consequence of iatrogenic arterial catheterization might be inadvertent embolization leading to (partial) infarction of the upper abdominal organs.

7.3.4 Contrast-induced renal insufficiency

Although the frequency of contrast-induced renal insufficiency has decreased by the use of non-ionic contrast, care should be taken to hydrate the patient adequately. Particularly in patients with an impaired food intake and/or diabetes mellitus this will also require adequate hydration (>2 l of fluid/24 h) prior to all angiographic procedures. If renal insufficiency develops, patients will complain about asthenia, vomiting may occur and oedema can be observed. The diagnosis is made by laboratory testing. Rehydration is generally sufficient. Care should be taken to prevent hyperkalemia to avoid cardiac rhythm abnormalities. To prevent nephrotoxicity, patients will be pre- and posthydrated according to the CBO-directive "Richtlijn Voorzorgsmaatregelen bij jodiumhoudende contrastmiddelen", page 23-26.

7.3.5 Thromboembolic events

It is known that patients with advanced malignant disease have an increased risk on the development of thromboembolic events especially in case of prolonged immobilization such as surgery or angiographic procedures. Prophylactic pressure stockings will be provided for all patients during the hospitalization period. No standard prophylactic anticoagulants will be provided due to the inherent risk of haemorrhages during invasive procedures.

8. METHODS

8.1 Study endpoints

8.1.1 Primary study endpoint

- The primary outcome is target lesions tumour response at three months follow-up. For this study, this is defined as: 1) complete response on CT at 3 months, or 2) partial response on CT at 3 months or 3) stable disease on CT at 3 months (see chapter 8.3.1 Definition of treatment success). Tumour size will be assessed on the portovenous phase of the dynamic contrast-enhanced CT images. At fixed intervals in time (3, 6, 9, and 12 months post ¹⁶⁶Ho-RE), the largest liver lesions are selected, to a maximum of two, and the maximum diameter in axial plane is measured. The sum of the maximum diameter of the lesions is recorded.
 - Complete Response (CR): disappearance of all lesions
 - Partial Response (PR): $\geq 30\%$ decrease in the sum of the longest diameters of target lesions, with the baseline measurements taken as reference
 - Stable Disease (SD): $<30\%$ decrease and $<20\%$ increase
 - Progressive Disease (PD): $\geq 20\%$ increase in the sum of the longest diameters of target lesions, with the baseline measurements taken as reference or appearance of new lesions

8.1.2 Secondary study endpoints

- To determine overall tumour response: (PET)CT will be used to quantify overall tumour response in time according to RECIST 1.1 guidelines. Antitumoural effect will also be assessed by relevant tumour markers (e.g. CEA for colorectal carcinoma and chromogranine A for neuroendocrine tumours) levels. Tumour marker changes will be expressed as a percentage of the pre-treatment values.
- To determine liver specific progression-free survival (LPFS). LPFS equals the interval between ¹⁶⁶Ho-RE and tumour progression in the liver according to RECIST 1.1. The protocol dictates that tumour response is measured on CT at 3, 6, 9, and 12 months post ¹⁶⁶Ho-RE. However, to obtain a true LPFS, CT of the liver for tumour response assessment can be performed at the physician's discretion in case of suspected tumour progression. LPFS is assessed overall (i.e., all patients treated in this study), and may be assessed separately for each primary tumour type
- To determine non-liver specific progression-free survival (NLPFS): at fixed intervals in time (3, 6, 9, and 12 months post ¹⁶⁶Ho-RE), and at the physician's discretion, (PET)/CT is performed for tumour response assessment. NLPFS is the time between ¹⁶⁶Ho-RE and tumour progression according to RECIST 1.1 for both intra- and extrahepatic tumours. NLPFS is assessed overall (i.e., all patients treated in this study), and may be assessed separately for each primary tumour type
- To assess overall survival. Date of death will be documented during the course of the study. After completion of study follow-up, survival will be checked through the central registration of the UMC Utrecht (Dutch: afdeling Zorgadministratie & -informatie) and / or the patient's general physician.
- To evaluate toxicity: the toxicity profile was the primary endpoint of the HEPAR I trial. In patients treated in the HEPAR II trial, the safety and toxicity of ¹⁶⁶Ho-RE will be further evaluated
- To evaluate QoL: Quality of live is evaluated using the EORTC questionnaire QLQ-C30 with colorectal liver metastases module QLQ-LMC21 (see Appendix VII). QoL is assessed at baseline, at 1 week, and at 1, 3, 6, and 12 months post ¹⁶⁶Ho-RE

- To assess performance status: using WHO performance status criteria. Performance status is assessed at every visit except for week 2
- To evaluate ^{99m}Tc -MAA and ^{166}Ho -PLLA-MS scout and therapy dose on SPECT/CT
- To evaluate ^{166}Ho -PLLA-MS scout dose and ^{166}Ho -PLLA-MS total dose on MRI. ^{166}Ho -PLLA-MS scout dose MRI will only be performed in the 7th – 12th patient undergoing treatment. After the 12th patient, patients will either receive ^{166}Ho -PET/CT imaging of the scout and therapy dose or ^{166}Ho -MR imaging of the scout dose
- To evaluate ^{166}Ho -PLLA-MS scout dose and ^{166}Ho -PLLA-MS total dose on PET/CT. ^{166}Ho -PET/CT will only be performed in the 1st – 6th patient. After the 12th patient, patients will either receive ^{166}Ho -PET/CT imaging of the scout and therapy dose or ^{166}Ho -MR imaging of the scout dose

8.2 Withdrawal of individual patients

Patients can abandon the study at any time for any reason if they wish to do so without any consequences for treatment or care. The investigator can decide to withdraw a patient from the study for urgent medical reasons.

Patients will be withdrawn from the study if:

- The investigator considers it in the best interest of the patient that he/she be withdrawn
- The patient withdraws consent
- The patient is unable to comply with protocol procedures

The date and reason for withdrawal must be recorded. If the patient withdraws consent after the therapy dose of ^{166}Ho -PLLA-MS has been administered, the patient will be advised to agree to follow-up safety investigations.

8.2.1 Replacement of withdrawn patients

All patients registered in the study will be accounted for. Patients who do not receive the therapy dose of ^{166}Ho -PLLA-MS will be replaced by another patient, and will not be included in any of the analyses. Based on the (sequential) design and criteria, recruitment and treatment will continue for the first cohort until 30 patients can be evaluated for tumour response. All patients that received ^{166}Ho -RE will be analysed for safety and secondary endpoints, regardless of their availability for tumour response evaluation. For example, a patient that drops out of the study 2 months post treatment will be evaluated for safety and secondary endpoints. However, this patient does not count as one of the 30 patients in whom tumour response needs to be evaluated in the first cohort. Therefore, the patient needs to be replaced. Consequently, if the study continues beyond 30 patients, recruitment will continue in cohorts of 6 patients that can be evaluated for tumour response.

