Prior to the procedure, the patient is offered a tranquilizer and a Foley catheter is inserted or a condom-catheter is applied for 24-hours urine collection. If a Foley catheter is used, the patient will receive a single dose of antibiotics 3 hours post ^{166}Ho -RE (therapy dose). An experienced interventional radiologist will administer the scout dose of ^{166}Ho -PLLA-MS through a catheter inside the hepatic artery at the position as planned during the first intervention. At the end of this angiography, the vascular sheath will remain in situ (femoral artery). This sheath will be used for the treatment angiography later that day. The vascular access site will be covered with a sterile patch. In addition, NaCl 0.9% under pressure will be connected to the sheath to prevent from clot formation. The patient will remain in supine position in his/her bed and will be transferred to the MRI / PET and SPECT scanners. In order to detect inadvertent administration to the lungs or other non-target organs (e.g. stomach, duodenum, pancreas) scintigraphy will be performed after administration of the scout dose of ^{166}Ho -PLLA-MS to assess its distribution. Both planar imaging of the thorax and abdomen will be performed, as well as SPECT of the abdomen. If the ^{166}Ho -PLLA-MS scout dose SPECT is suspect for extrahepatic deposition, after a week a second $^{99\text{m}}\text{Tc}$ -MAA procedure will be started. In this procedure the blood vessels that probably cause the extrahepatic deposition will be identified if possible. Based on the findings, the interventional radiologist might adapt the catheter position and/or coil the culprit extrahepatic vessels. In case the second $^{99\text{m}}\text{Tc}$ -MAA SPECT does not show extrahepatic deposition, a new ^{166}Ho -PLLA-MS scout dose will be administered. In case this second ^{166}Ho -PLLA-MS scout dose SPECT does not show extrahepatic deposition the ^{166}Ho -PLLA-MS therapy dose will be given. If again extrahepatic ^{166}Ho -PLLA-MS scout dose deposition occurs, the treatment will be terminated.

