8.4 Independent Data Monitoring Committee (IDMC)

An IDMC is established. The IDMC is an independent group comprising internal members (from within the UMCU) and external members. This phase II study is open label and patients are individually closely monitored for safety, as was done in the HEPAR I study. The main objective is to decide whether or not to embark on a larger phase III trial. Hence it was considered adequate to establish an IDMC with both (independent) internal UMCU members as well as an external member. In case of a future phase III trial, a fully external IDMC is strongly recommended. The IDMC includes the following members:

- Dr. [name], Meander Medical Center Amersfoort; nuclear medicine physician
- Dr. [name], University Medical Center Utrecht; gastro-enterologist
- Dr. [name], Albert Schweitzer ziekenhuis; interventional radiologist
- Dr. [name], Julius Center Health Sciences and Primary Care Utrecht; biostatistician

The IDMC will analyse preliminary study results on tumour response after the first 30 patients who are amenable for tumour response assessment at 3 months (i.e. PPS), and every 6 patients who are amenable for tumour response assessment at 3 months thereafter (see Table 5). Waiting for the three-month follow-up of all 30/36/42/48 patients is only required if, based on the available follow-up in the other patients, it remains uncertain whether the stopping boundaries will be reached.

The IDMC analyse preliminary study results on safety as well (see Table 5). In contrast to the tumour response analyses, the safety analyses will include all patients that received treatment within a time span of 3 months (regardless of their availability for tumour response assessment, i.e. FAS), and therefore, these reviews may not run in sync with the IDMC tumour response analyses. Patient inclusion and treatment may continue during IDMC safety analyses. In its safety analyses, the IDMC will consider specifically the reasons and potential consequences on treatment benefit of the patients that discontinued before the 3 months assessment. The IDMC will receive reports on a regular basis on all SAEs reported for this trial and a complete summary safety report for each safety analysis. The IDMC will work according to the IDMC charter (see Appendix VIII) Recruitment will not be interrupted unless otherwise requested by the IDMC Chairman.

The responsibilities of the IDMC include:

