9.2.3 Adverse events (AEs)

Adverse events are defined as any untoward medical occurrence, unintended disease or injury or any untoward clinical signs (including an abnormal laboratory finding) in subjects, users or other persons whether or not related to the investigational device (Ho-166 poly lactic acid microspheres). This also includes events related to the procedures involved (any procedure specified in the clinical investigation plan).

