9.4 Documentation

Attention is to be paid to the occurrence of AEs at all stages of the examination. Thus, the patient should be closely observed by the investigator both during and after the treatment. The recording phase for AEs will start with the first study drug administration and will end the last day of the follow-up period. AEs related to hematological or renal toxicity which are still present at the end of the follow-up period will be followed up until complete resolution as assessed by the investigator. Any adverse events have to be documented in detail as indicated on the E-CRF. The following information is required:

- The date and **time of onset** of any AEs
- The **duration** (the entire duration of an event or symptom, calculated from date of onset and date of end)
- The maximum **intensity** (mild, moderate or severe; for definitions, see below).
- The **drug relationship** of the AE to the investigational product (for definitions, see below)
- Any **study drug action taken** and any other **action taken** by the investigator to resolve the adverse events (entered in free text)
- The **outcome** of the adverse event (recovered completely, recovered with residual effects, continuing).
- An assessment of the **seriousness** of the event will be made by the investigator.

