10. STATISTICAL ANALYSIS

Two sets of study data will be evaluated: the Full Analysis Set (FAS) and the Per Protocol Set (PPS). The FAS is defined as the set of data generated from all included patients who received the therapy dose. The PPS is defined as the set of data generated from the included patients who complied with the protocol up to at least 3 months of follow-up. All analyses will be performed for the FAS. Analyses to assess tumour response and explore and understand the direct effects of therapy will be based on the PPS.

The primary analysis will be the evaluation of the number and percentage of patients with target lesions tumour response, according to the group sequential decision criteria as given in chapter 3. In addition, the estimated response percentage and appropriate 95% confidence interval will be presented. Further description in numbers and percentages with complete response, partial response, stable disease and progressive disease will be provided. For the tumour response decision, this analysis is primarily based on the PPS set as defined above. However, the analysis based on the FAS will also be performed. In that case, a conservative imputation on target lesions tumour response will be done for those patients that did not reach their 3 months of follow-up (e.g., if a patient died before 3 months or stopped because of disability reasons it will be classified as failure).

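### Patients who undergo study angiography or receive a holmium scout dose but not the therapy dose are left out of every aggregate safety table.

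*Protocol*

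**What the plan says.** Section 8.2.1 provides that patients who do not receive the therapy dose "will be replaced by another patient, and will not be included in any of the analyses". It makes no exception for safety.

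Section 10 defines the set to match: "The FAS is defined as the set of data generated from all included patients who received the therapy dose". It adds: "All analyses will be performed for the FAS". Section 8.4 bases the IDMC safety reviews on treated patients, "regardless of their availability for tumour response assessment, i.e. FAS", and the footnote to Table 5 repeats this. No other safety set is defined.

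On exposure before the therapy dose, section 5.2.2 describes angiography, coiling and the technetium-99m-labelled albumin (MAA) injection. It bars the scout and therapy doses if extrahepatic deposition cannot be corrected or the lung shunt exceeds 20%. Section 5.2.3 describes the holmium scout dose. If a first scout scan suggests extrahepatic deposition, a second MAA procedure is started, and a second scout dose follows if that scan is clean. If extrahepatic "scout dose deposition occurs, the treatment will be terminated".

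On adverse events, section 9.2.3 says of its definition: "This also includes events related to the procedures involved (any procedure specified in the clinical investigation plan". Section 9.4 says: "The recording phase for AEs will start with the first study drug administration". Table 2 and section 5.2.2 already monitor adverse events at the pretreatment visit.

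**The concern.** Toxicity is a secondary endpoint, reported under section 10.2 as counts and percentages. Section 12.8 says that the data will support a CE-marking application. A patient stopped before the therapy dose has still had arterial catheterisation and contrast, and may have had the investigational device itself: section 9.2.1 defines the device as the holmium microspheres, which is what a scout dose contains. Several complications listed in section 7.3, such as access-site haematoma, arterial dissection, contrast-induced renal insufficiency and thromboembolism, do not need a therapy dose to occur.

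The exclusion also depends on what happened to the patient. Some patients leave the tables because a study procedure showed extrahepatic deposition, the hazard to which section 7.2 is devoted. They are missing from both numerator and denominator, so the safety tables describe only those who passed every earlier stage.

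**Working it through.** **Does the exclusion cover safety?** Three statements point the same way. Section 8.2.1 removes these patients from all analyses. Section 10 makes receipt of the therapy dose the entry condition for the FAS. Section 8.4 and Table 5 use the FAS for safety. Section 8.2.1 later says that all patients who received holmium radioembolization are analysed for safety. That does not bring scout-only patients back, because section 5.2.3 equates that term with the therapy dose and the earlier sentence has already excluded them.

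**Who is excluded, and after what exposure?**

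| Stopped because of | Exposure by then | In FAS? |
|---|---|---|
| Uncorrectable extrahepatic MAA deposition, or lung shunt above 20% | Angiography, coiling where needed, MAA | No |
| Second extrahepatic scout deposition | The above, a repeat MAA procedure and two scout doses | No |
| Withdrawal before the therapy dose | Any of the above | No |
| Not stopped: first scout deposition corrected, then therapy dose | All stages | Yes |
| Not stopped: deposition seen only after the therapy dose | All stages | Yes |

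**How many?** The protocol gives no rate of stopping before therapy, so a rate *d* has to be assumed. With *n* treated patients, the number omitted is n/(1 − d) − n.

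- n = 30, d = 10%: 30/0.9 − 30 = 3.3
- n = 48, d = 20%: 48/0.8 − 48 = 12

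This gives about 3 to 12 patients. A wider assumption of 5–25%, rounding the total up to whole patients, gives 2 to 10 omitted beside 30 treated and 3 to 16 beside 48.

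**What could it do to a reported rate?** The counts here are invented for illustration. Suppose 5 patients stop early, one of them has a procedural adverse event, and none of the 30 treated patients has that event.

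- As planned: 0/30. The exact two-sided 95% upper limit is 1 − 0.025^(1/30) = 11.6%.
- All exposed patients: 1/35 = 2.9%, exact upper limit 14.9%.

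**Does a pooled denominator suit every purpose?** No. Section 8.4 guides the IDMC by bilirubin or factor V toxicity of grade 3–4 in more than 30% of patients, and by other grade 3–4 events in up to 50%. Take 10 such bilirubin or factor V events among 30 treated patients: 10/30 = 33.3%, above 30%. Adding 5 patients without the therapy dose gives 10/35 = 28.6%, below it.

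**Is the efficacy design touched?** No. An exact binomial calculation with the Table 1 boundaries gives a one-sided type I error of 4.52% (stated 4.5%) and power of 89.8% (stated 90%). Neither depends on the safety set.

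**When does adverse event recording start?** Section 9.4 ties it to the first administration of study drug. Even if that includes MAA, section 5.2.2 gives MAA after angiography and coiling, so events during those procedures come before the stated start. Table 2, section 5.2.2, section 9.2.3 and the Summary's statement that adverse events are recorded throughout all imply an earlier start.

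**The case against.** The strongest reply is that oversight does not depend on the FAS. Section 8.2.1 accounts for every registered patient, section 8.2 records the date and reason for withdrawal, and sections 8.4 and 9.3 send serious events to the IDMC, the ethics committee and the competent authority without restriction to treated patients. This stands, so the cases are not hidden from oversight. It covers serious events case by case, however. It supplies neither the non-serious events nor a rate over all exposed patients.

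A reader might infer that the tables lose exactly the non-target deposition cases. They do not. A first scout deposition that is corrected, and deposition found only after therapy, both stay in the FAS, while the excluded group also holds lung-shunt exclusions and withdrawals.

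A reader might also infer that the main device risk is understated by rule. The protocol does not show that. The Introduction calls the scout dose small, these patients never receive the therapy dose, and deposition on a scan is not in itself an adverse event under section 9.2.3. Nor is the direction of the effect fixed: for the IDMC guides, adding untreated patients would lower the percentages.

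It is also fair to say that the section 9.4 conflict is the smaller part, since that section itself asks for attention to adverse events at all stages and the schedule already collects them at pretreatment.

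**Conclusion.** The point holds as a should-fix. Followed as written, the protocol produces aggregate safety tables that omit patients exposed to study procedures and, in some cases, to the investigational device, including every patient whose treatment was stopped for uncorrectable or recurrent extrahepatic deposition. The exclusion is a rule fixed in the protocol; an analysis plan with a wider safety set would contradict it.

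The size cannot be derived from the document. The figure of about 3 to 12 omitted patients rests wholly on the assumed 10–20% rate, and the patients who received a scout dose are only part of that group. The damage is confined to the descriptive safety results. The wording in section 9.4 is a real but lesser contradiction.

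**What to change.** 1. In section 8.2.1, exclude patients without the therapy dose from the efficacy analyses only.
2. In section 10, add a safety set of all patients who started a study procedure, or at minimum all who received a scout dose. Tabulate adverse events by furthest stage reached: angiography and MAA only, scout dose, therapy dose. Give this table to the IDMC.
3. In section 8.4, state that the 30% and 50% toxicity guides keep therapy-dose recipients as their denominator, so that they are not diluted.
4. Reconcile the start of adverse event recording in section 9.4 with Table 2 and sections 5.2.2 and 9.2.3.

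The cost is wording and a few more table rows, with a possibly slightly less favourable procedural safety profile. Follow-up of the added patients may be short: section 8.2 addresses safety follow-up after withdrawal of consent only for those who had the therapy dose, and Table 2 has no separate schedule for patients stopped earlier. The tables should therefore state how long each group was observed. Sample size and stopping boundaries do not change.
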